10.6 Frequency of review of cumulative data

Annual reports will be made to the Penn State IRB as per the current protocol. Data will also be monitored by the Public Health Sciences department periodically.

10.7 Statistical tests

A Pearson's chi-square test, or Fisher's exact test if the expected cell counts are <5, will be used to compare each reported AE between the Lipiodol UF® and saline groups, provided there are sufficient AEs to obtain inference.

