1.0 Objectives

1.1 Study Objectives

The primary objective is to collect the ongoing pregnancy rate among subjects in the study. The co-primary objective is observe the safety and tolerability of Lipiodol UF®. Secondary objectives will be to document the relative pain during the Sono HSG procedure and any changes in quality of life as a result of the procedure according to the contrast agent. Exploratory outcomes will be the feasibility of blinding the patient and observer to the type of contrast medium injected at the end of the Sono HSG procedure and the prevalence of Anti-Chlamydial antibodies and association with outcomes. The results from this pilot trial will guide the design of a larger multi-center clinical trial examining Lipiodol UF® as a contrast agent during Sono HSG.

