2.3 Study Rationale

The rationale for this trial is to further explore the use of oil based contrast media, specifically Lipiodol UF® both in the context of a contrast agent and as a potential treatment agent for women from couples with infertility. We specifically propose, eventually, to both build on and replicate the H2Oilie trial conducted in the Netherlands. We will build on the H2Oilie trial by utilizing ultrasound instead of fluoroscopy to conduct our HSG. Ultrasound based hysterosalpingography, i.e. Sono HSG, can be conducted in an outpatient setting by a single physician. It avoids patient and physician exposure to radiation, in many cases the additional trip to an inpatient hospital, the requirement of staffing by both radiologic and gynecologic personnel, and the greater expense of fluoroscopic HSG. We will expand the patient population from primarily women with unexplained infertility, to all women with infertility who will receive expectant management or conventional first line therapies. We will exclude women who will be going on to in vitro fertilization (IVF) as the chosen infertility therapy, because IVF as a first line

therapy is only applicable to women with tubal occlusion/tubal disease or couples with severe oligospermia requiring oocyte insemination or intracytoplasmic sperm injection (ICSI).

Our specific hypothesis is that tubal patency testing by Sono HSG with an oil-based contrast medium, Lipiodol UF®, will lead to higher ongoing pregnancy rates compared to the use of normal saline as a contrast medium with equal safety as a saline contrast agent.

The intervention will involve injection of 10 cc of Lipiodol UF® versus saline at the time of Sono HSG as a control. Lipiodol UF® is approved as an injection agent for HSG by the U.S. FDA.

The underlying rational for the pilot trial is to obtain preliminary data and to pilot the methodology to conduct a larger multi-center trial definitively powered to document the safety and efficacy of Lipiodol UF® as a primary contrast agent during Sono HSG.

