8.0 Subject Numbers and Statistical Plan

8.1 Number of Subjects

Fifty-six subjects will be randomized and receive study intervention, twenty-eight per randomization arm. We estimate that we will need to screen one hundred patients in order to meet this goal.

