8.2 Sample size determination

For pilot studies it has been suggested that sample sizes ranging anywhere from 12 to 60 subjects per group would provide sufficient data to obtain estimates of the primary outcome in order to power a future definitive clinical trial, as well as provide sufficient evidence to assess feasibility, blinding safety, and regulatory considerations.(16) A sample size of 50 evaluable subjects (25 per group) should be sufficient in order to satisfy the goals of this pilot study (i.e., feasibility of binding the contrast medium, obtaining estimates for a formal power calculation of a future trial, and evaluating the safety of the contrast medium). We anticipate, however, that 10% of the subjects will either drop-out prior to study completion or be randomized but not be able to have a Sono HSG performed because they change their minds during the procedure and opt out or they have bilateral tubal occlusion or a hydrosalpinx. Also, subjects may not be evaluable as result of technical errors associated with manipulation of the required glass syringe for study drug administration. Therefore, we will recruit a minimum of 60 subjects up to a maximum of 72 subjects, terminating enrollment once we have reached the goal of 50 evaluable subjects.

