8.3 Statistical methods

The analysis dataset will follow a modified intention to treat (mITT) where all evaluable subjects will be analyzed. For the pilot study, an evaluable subject is a subject that has been randomized and has completed the Sono HSG.

Descriptive statistics for continuous data will be reported as the mean (standard deviation) or as the median (25th percentile, 75th percentile) if the distribution is not normally distributed. Descriptive statistics for categorical will be reported as a frequency and percentage. All hypothesis tests will be two-sided and tested at a significance level of 0.05. All analyses will be conducted using SAS software, version 9.4 (SAS Institute Inc., Cary, NC) or R software, version 3.3.3 (R Foundation for Statistical Computing, Vienna, Austria).

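### The equal-safety hypothesis is paired with an AE comparison made of conditional per-term significance tests, with no effect estimate, interval or margin

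*Combined protocol and SAP*

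**What the plan says.** Three places set the aim:

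- **Section 1.1** gives safety co-primary status, worded as observation: "The co-primary objective is observe the safety and tolerability of Lipiodol UF".
- **Section 2.3** puts safety inside the specific hypothesis. Lipiodol UF is to give higher ongoing pregnancy rates "with equal safety as a saline contrast agent".
- **Section 8.2** states that "A sample size of 50 evaluable subjects (25 per group) should be sufficient in order to satisfy the goals of this pilot study", and lists among those goals "obtaining estimates for a formal power calculation of a future trial, and evaluating the safety of the contrast medium".

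The analysis is set elsewhere:

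- **Section 10.7** is the whole of the planned between-arm AE comparison. A Pearson chi-square test, or Fisher's exact test when expected counts fall below 5, "will be used to compare each reported AE between the Lipiodol UF® and saline groups, provided there are sufficient AEs to obtain inference". How many events would be enough is not defined.
- **Section 8.3** adds the error rate: "All hypothesis tests will be two-sided and tested at a significance level of 0.05". It also provides frequencies and percentages for categorical data.
- **Section 10.2** names VAS discomfort as a primary safety parameter alongside serious sequelae. **Section 8.3.2** compares VAS by t-test (or a transformation or rank-sum test), with a difference in means and 95% CI for the t-test.
- **Sections 8.3.1 and 8.3.2** attach a relative risk and 95% CI to ongoing pregnancy and to live birth. Section 10.7 attaches nothing comparable to AEs.

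**The concern.** A test of difference can show that two arms differ. When it is not significant, it does not show that they are alike. That conclusion needs an interval judged against a margin, and no safety analysis in the plan has a margin.

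Two features of section 10.7 make this worse. Testing term by term spreads a small number of events over many small tables. The proviso then drops the comparison where events are sparse, which is likely for the harms that sections 2.1 and 11.0 worry about most: intravasation, embolization, granuloma and allergic reaction.

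The likely AE result is therefore a set of non-significant p-values, or no test at all, next to a hypothesis of equal safety. Section 1.1 says the results will guide the design of a larger trial. That trial needs AE rates with their uncertainty in order to set a margin and a sample size, and section 10.7 does not commit to supplying them.

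**Working it through.** **Inputs from the documents.** 50 evaluable women, 25 per group (8.2); 10% loss (8.2); 56 randomized, 28 per arm (8.1); two-sided 0.05 (8.3); the chi-square/Fisher rule (10.7). The documents give no AE rate, safety margin or safety power, so every AE rate and margin below is an assumption.

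**1. The plan's own figure.** 50 / (1 − 0.10) = 55.6, rounded up to 56. This reproduces section 8.1. There is no safety calculation to reproduce.

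**2. Power of the plan's rule.** Power = Σ over a, b of Bin(a; n, p_L) × Bin(b; n, p_S) × I(the rule rejects at 0.05). Here a and b are the event counts on Lipiodol and saline. The rule is uncorrected Pearson chi-square, with Fisher when any expected count is below 5.

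| Assumed rate, saline v Lipiodol | 25 per arm | 28 per arm |
|---|---|---|
| 4% v 12% | 3.6% | 4.4% |
| 4% v 20% | 24.4% | 26.8% |
| 0% v 20% | 38.3% | 49.9% |
| 10% v 30% | 40.9% | 42.2% |

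For 80% power at 25 per arm, the Lipiodol rate must reach about 30% if saline is near 0%, 36.5% if saline is 5%, and 43.5% if saline is 10%.

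**3. A split on the edge of significance.** For 5/25 v 0/25 the expected event count is 2.5 per arm, so Fisher applies:

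p = 2 × C(25,5) / C(50,5) = 2 × 53,130 / 2,118,760 = 0.0502, not significant.

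Wilson limits are 8.9% to 39.1% for 5/25 and 0% to 13.3% for 0/25. The Newcombe limits for the 20-point difference are then:

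- lower: 0.200 − √[(0.200 − 0.0886)² + 0.1332²] = +0.026
- upper: 0.200 + (0.3913 − 0.200) = +0.391

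The test would be reported as non-significant, while the interval runs from +2.6 to +39.1 points. Against no saline events, the smallest significant count is 6/25 (p = 0.022).

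**4. No events at all.** For 0/25 the two-sided 95% Clopper-Pearson upper limit is 1 − 0.025^(1/25) = 13.7%. For 0/28 it is 12.3%. For 0/25 v 0/25 the Newcombe interval is −13.3 to +13.3 points. An event with a true rate of 5% is absent from 25 women with probability 0.95^25 = 28%.

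**5. What a margin would need.** For non-inferiority with equal true rates, one-sided 0.025 and 80% power, n per arm = (1.960 + 0.842)² × 2p(1 − p) / margin², a normal approximation.

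| Assumed AE rate | Margin 10 points | Margin 15 points | Margin 20 points |
|---|---|---|---|
| 5% | 75 | 34 | 19 |
| 10% | 142 | 63 | 36 |

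At 25 or 28 per arm, only the 20-point margin at a 5% rate is within reach.

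**6. VAS.** The 95% CI half-width is about 1.96 × √(2/25) = 0.55 SD. This is a usable estimate, but with no margin it does not support equality either.

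**The case against.** The strongest reply is that this is a pilot and says so. Section 1.1 asks only to observe safety. Section 2.3 leaves definitive documentation of safety to a larger trial. The sufficiency statement in section 8.2 concerns pilot goals and does not say that 25 per group can show equality. Nowhere does the plan say that a non-significant AE test will be read as equal safety, and declining to test sparse events is sensible practice. All of this stands, and it rules out treating low power as the defect.

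A reader might also infer two stronger things that the documents do not support:

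- **That safety is assessed only by per-event tests.** It is not. VAS discomfort is a primary safety parameter (10.2) with a planned mean difference and 95% CI (8.3.2), and that analysis does not depend on event counts.
- **That nothing would be known by arm when events are few.** Section 8.3 covers frequencies and percentages, and section 10.3 records every AE with severity and relationship to study product. The proviso in section 10.7 removes the test, not the counts. A reader could work out an interval from those counts.

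What the reply does not remove is that section 2.3 still states equality as part of the trial's hypothesis, while section 10.7 offers AEs only conditional tests of difference, without the effect estimate and CI planned for pregnancy, live birth and VAS. If the pilot's purpose is to estimate, that argues for intervals rather than against them.

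**Conclusion.** The point holds in a limited form. The fault is the pairing of an equality hypothesis, and a statement that 25 per group suffices for "evaluating the safety of the contrast medium", with an AE analysis that cannot support equality and commits to no interval. At 25 per arm, the plan's rule would miss assumed excesses of 16 to 20 points more often than not (power 24% to 41%). A clean arm of 0/25 would still be compatible with a true rate of up to 13.7%. Using 28 per arm changes little: power for the same excesses is 27% to 50%.

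The power figures rest on assumed AE rates, and the sample sizes also on assumed margins. The p-value and intervals for the example splits depend only on 25 per arm. The documents do not support concluding that the trial is too small for a pilot, or that the investigators plan to claim equal safety from it. The change is worth making, because the data are already being collected and the larger trial depends on these estimates.

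**What to change.** **Section 10.7.** Replace the conditional per-term tests with a fixed summary. Give, per arm, the number of women with at least one procedure-related AE and the number with at least one SAE, each with the risk difference and a 95% CI (Newcombe or exact), whatever the event count. List individual AE terms descriptively by arm. Add one line on what counts as procedure-related, since section 10.3 records relationship to study product.

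**Sections 2.3 and 8.2.** Say that the pilot estimates AE rates to a stated precision (for example, 0/25 leaves an upper limit of 13.7%), and that a non-significant difference is not evidence of equal safety. Leave the equal-safety hypothesis to the larger trial, with a prespecified margin.

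**Cost.** A few sentences, with no added patients, visits or data. The downside is that the stated safety claim becomes less favourable.

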10.8 Suspension of research

This study may be temporarily suspended or prematurely terminated if there is sufficient reasonable cause. Written notification, documenting the reason for study suspension or termination, will be provided by the suspending or terminating party to Guerbet LLC, Princeton, NJ. If the study is prematurely terminated or suspended, the PI will promptly inform the IRB and will provide the reason(s) for the termination or suspension. Study may resume once concerns about safety, protocol compliance, data quality are addressed and satisfy the involved party (i.e. investigators, IRB, sponsors). There are no planned stopping rules as we are using an FDA approved contrast agent for its approved indication.

11.0 Risks

The immediate risks of Lipiodol UF® for HSG are lower than the other indicated uses, since the major risks are related to intravasation and associated anaphylactic and/or embolism events. While there is evidence of intravasation during conventional fluoroscopic HSG(10), there has been only one case report of a cerebral embolization event related to this, with a 12 day coma and ICU stay after HSG that resolved without sequelae. (11). The immediate risks include discomfort or pain from the infusion into the uterine cavity, an anaphylactic or allergic reaction to Lipiodol UF®, and embolization after intravasation. The long term risks include formation of granulomas and/or pelvic adhesions and late sequelae of intravastion.

There is a risk of loss of confidentiality if information is obtained by someone other than the investigators. Precautions will be taken to prevent this as described in Section 9.

There is a risk that the questionnaires may make participant uncomfortable.

Risks of standard venipuncture include slight pinch or pin prick, discomfort, black and blue mark at the site of puncture, small blood clot, infection or bleeding at the site, and fainting during the procedure.

Risks associated with Sonohysterogram/Hysterosalpingogram include pain, bleeding, damage to the uterus, pelvic infection, interrupting an unrecognized pregnancy, small amount of radiation exposure, and allergic reaction to the radio-opaque dye.

Risks associated with randomization. One treatment may be less effective or have more side effects than the other research treatment or other available treatments.

12.0 Potential Benefits to Subjects and Others

12.1 Potential Benefits to Subjects

There is no guarantee that subjects will benefit from this research. The potential benefit is an increased chance for ongoing pregnancy and live birth for women desiring children who undergo the test.

12.2 Potential Benefits to Others

The results of this research may guide the future practice of this test by establishing a more effective and tolerable procedure by using lipid based oil medium for sonographic based hysterosalpingography (Sono HSG) compared to water based contrast for women seeking fertility.

13.0 Sharing Results with Subjects

We will share the overall results of the study and the study agent assignment with all patients at study closure.

14.0 Subject Stipend (Compensation) and/or Travel Reimbursements

Participants who complete the FertiQol at final study contact, will receive a \$10 gift card. .

15.0 Economic Burden to Subjects

15.1 Costs

Participants will not be charged for the cost of any tests or procedures that are required as part of the research and are outside the standard of care including all study required blood tests and the lipid oil which will be provided by the sponsor at no cost. Participants and/or their insurance companies will be responsible for costs of medical services for care they would receive even if they were not in this study including routine medications, tests and procedures, co-payments/co-insurance/deductibles. Routine tests and procedures will be billed in the usual manner and participant will be responsible for any charges not reimbursed by their insurance company.

15.2 Compensation for research-related injury

It is the policy of the institution to provide neither financial compensation nor free medical treatment for research-related injury. In the event of injury resulting from this research, medical treatment is available but will be provided at the usual charge. Costs for the treatment of research-related injuries will be charged to subjects or their insurance carriers.

16.0 Resources Available

16.1 Facilities and locations

Participant visits and Sono HSG will occur at the infertility clinic at [name] on the Hershey Medical Center campus.

16.2 Feasibility of recruiting the required number of subjects

Patients will be recruited from the practice at Penn State Hershey by the investigators and study personnel. We perform 10-15 Sono HSGs per month for fertility testing and it is anticipated that almost all patients will be eligible as the criteria for study inclusion overlap with our criteria for fertility testing. We project a high rate of recruitment of eligible patients into the trial. However with a conservative estimate that 50% of patients undergoing Sono HSG for fertility testing opt to participate in the study we estimate 5-7 patients per month will be enrolled. Thus it will take conservatively 7-10 months to recruit the cohort and according to our best estimate, 6 months. We do not anticipate difficulty in following patients since they will be receiving fertility treatment immediately after the Sono HSG through our practice.

16.3 PI Time devoted to conducting the research

The PI is the Vice Chair of Research in the Department of OB/GYN and has one full day per week dedicated to research.

16.4 Availability of medical or psychological resources

Participants will be receiving routine care and infertility treatment.

16.5 Process for informing Study Team

There are 2 weekly meetings within the Division of Reproductive Endocrinology attended by the physicians and research coordinators. One is dedicated entirely to research, and the other is dedicated to clinic. Research recruitment and updates are covered at both of these meetings. Study coordinators are cross trained on the REI study protocols.

17.0 Other Approvals

17.1 Other Approvals from External Entities

Not Applicable

17.2 Internal PSU Committee Approvals

Check all that apply:

- Anatomic Pathology – Hershey only – Research involves the collection of tissues or use of pathologic specimens. Upload a copy of HRP-902 - Human Tissue For Research Form on the “Supporting Documents” page in CATS IRB. This form is available in the CATS IRB Library.
- Animal Care and Use – All campuses – Human research involves animals and humans or the use of human tissues in animals
- Biosafety – All campuses – Research involves biohazardous materials (human biological specimens in a PSU research lab, biological toxins, carcinogens, infectious agents, recombinant viruses or DNA or gene therapy).
- Clinical Laboratories – Hershey only – Collection, processing and/or storage of extra tubes of body fluid specimens for research purposes by the Clinical Laboratories; and/or use of body fluids that had been collected for clinical purposes, but are no longer needed for clinical use. Upload a copy of HRP-901 - Human Body Fluids for Research Form on the “Supporting Documents” page in CATS IRB. This form is available in the CATS IRB Library.
- Clinical Research Center (CRC) Advisory Committee – All campuses – Research involves the use of CRC services in any way.
- Conflict of Interest Review – All campuses – Research has one or more of study team members indicated as having a financial interest.
- Radiation Safety – Hershey only – Research involves research-related radiation procedures. All research involving radiation procedures (standard of care and/or research-related) must upload a copy of HRP-903 - Radiation Review Form on the “Supporting Documents” page in CATS IRB. This form is available in the CATS IRB Library.
- IND/IDE Audit – All campuses – Research in which the PSU researcher holds the IND or IDE or intends to hold the IND or IDE.
- Scientific Review – Hershey only – All investigator-written research studies requiring review by the convened IRB must provide documentation of scientific review with the IRB submission. The scientific review requirement may be fulfilled by one of the following: (1) external peer-review process; (2) department/institute scientific review committee; or (3) scientific review by the Clinical Research Center Advisory committee. NOTE: Review by the Penn State Hershey Cancer Institute Scientific Review Committee is required if the study involves cancer prevention studies or cancer patients, records and/or tissues. For more information about this requirement see the IRB website at: <http://www.pennstatehershey.org/web/irb/home/resources/investigator>

18.0 Multi-Site Research

Not Applicable

19.0 Adverse Event Reporting

19.1 Reporting Adverse Reactions and Unanticipated Problems to the Responsible IRB

In accordance with applicable policies of The Pennsylvania State University Institutional Review Board (IRB), the investigator will report, to the IRB, any observed or reported harm (adverse event) experienced by a subject or other individual, which in the opinion of the investigator is determined to be (1) unexpected; and (2) probably related to the research procedures. Harms (adverse events) will be submitted to the IRB in accordance with the IRB policies and procedures.

